**ALGORITHM FOR CONCOMITANT ILLNESSES:**

START DATE	STOP DATE	ACTION
Known	Known	If stop date > date of first treatment dose and start date <= date of first treatment dose, assign as concomitant illness
	Partial	Impute stop date as latest possible date (i.e. last day of month if day unknown or 31st December if day and month are unknown), then: If stop date > date of first treatment dose and start date <= date of first treatment dose, assign as concomitant illness
	Missing	If stop date is missing then assume concomitant illness
Partial	Known	Impute start date as earliest possible date (i.e. first day of month if day unknown or 1st January if day and month are unknown), then: If stop date > date of first treatment dose and start date <= date of first treatment dose, assign as concomitant illness
	Partial	Impute start date as earliest possible date (i.e. first day of month if day unknown or 1st January if day and month are unknown) and impute stop date as latest possible date (i.e. last day of month if day unknown or 31st December if day and month are unknown), then: If stop date > date of first treatment dose and start date <= date of first treatment dose, assign as concomitant illness
	Missing	Impute start date as earliest possible date (i.e. first day of month if day unknown or 1st January if day and month are unknown), then: If stop date is missing then assume concomitant illness
Missing	Known	If stop date > date of first treatment dose, assign as concomitant illness

START DATE	STOP DATE	ACTION
	Partial	Impute stop date as latest possible date (i.e. last day of month if day unknown or 31st December if day and month are unknown), then: If stop date > date of first treatment dose, assign as concomitant illness
	Missing	If stop date is missing then assume concomitant illness

[REDACTED]

[REDACTED]

[REDACTED]

[REDACTED]

[REDACTED]

APPENDIX 3. ANNOTATED EXACT FOR RAW SCORE ASSIGNMENT

1. Did your chest feel congested today?	0. Not at all
	1. Slightly
	2. Moderately
	3. Severely
	4. Extremely
2. How often did you cough today?	0. Not at all
	1. Rarely
	2. Occasionally
	3. Frequently
	4. Almost constantly
3. How much mucus (phlegm) did you bring up when coughing today?	0. None at all
	1. A little
	1. Some
	2. A great deal
	3. A very great deal
4. How difficult was it to bring up mucus (phlegm) today?	0. Not at all
	1. Slightly
	2. Moderately
	3. Quite a bit
	4. Extremely
5. Did you have chest discomfort today?	0. Not at all
	1. Slight
	2. Moderate
	3. Severe
	4. Extreme
6. Did your chest feel tight today?	0. Not at all
	1. Slightly
	2. Moderately
	3. Severely
	4. Extremely
7. Were you breathless today?	0. Not at all
	1. Slightly
	2. Moderately
	3. Severely
	4. Extremely
8. Describe how breathless you were today	0. Unaware of breathlessness

	1.Breathless during strenuous activity
	2.Breathless during light activity
	3.Breathless when washing or dressing
	3.Present when resting
9. Were you short of breath today when performing your usual personal care activities like washing or dressing?	0.Not at all
	1.Slightly
	2.Moderately
	3.Severely
	3.Extremely
	4.Too breathless to do these
10. Were you short of breath today when performing your usual indoor activities like cleaning or household work?	0.Not at all
	1.Slightly
	2.Moderately
	3.Severely
	3.Extremely
	3.Too breathless to do these
11. Were you short of breath today when performing your usual activities outside the home such as yard work or errands?	0.Not at all
	1.Slightly
	2.Moderately
	3.Severely
	3.Extremely
	3.Too breathless to do these
12. Were you tired or weak today?	0.Not at all
	1.Slightly
	2.Moderately
	3.Severely
	4.Extremely
13. Last night, was your sleep disturbed?	0.Not at all
	1.Slightly
	2.Moderately
	3.Severely
	4.Extremely
14. How scared or worried were you about your lung problems today?	0.Not at all
	1.Slightly
	2.Moderately
	3.Severely
	3.Extremely

[REDACTED]

[REDACTED]

[REDACTED]

[REDACTED]

[REDACTED]

APPENDIX 4. RAW SUMMED SCORE TO SCALE CONVERSION TABLE FOR EXACT TOTAL SCORE

Raw Summed Score	EXACT Total Score	Raw Summed Score	EXACT Total Score
0	0	26	50
1	8	27	51
2	13	28	52
3	17	29	53
4	20	30	54
5	23	31	55
6	25	32	57
7	27	33	58
8	28	34	59
9	30	35	60
10	31	36	61
11	33	37	63
12	34	38	64
13	36	39	65
14	37	40	67
15	38	41	68
16	39	42	70
17	40	43	72
18	41	44	73
19	42	45	75
20	43	46	77
21	44	47	80
22	46	48	83
23	47	49	87
24	48	50	92
25	49	51	100

[REDACTED]
 [REDACTED]
 [REDACTED]
 [REDACTED]

APPENDIX 5. SGRQ ITEM WEIGHTS

Question	Answers	Weight
Part 1		
Question 1: Over the past 4 weeks, I have coughed	Almost every day	80.6
	Several days a week	63.2
	A few days a month	29.3
	Only with respiratory infections	28.1
	Not at all	0.0
Question 2: Over the past 4 weeks, I have brought up phlegm (sputum)	Almost every day	76.8
	Several days a week	60.0
	A few days a month	34.0
	Only with respiratory infections	30.2
	Not at all	0.0
Question 3: Over the past 4 weeks, I have shortness of breath	Almost every day	87.2
	Several days a week	71.4
	A few days a month	43.7
	Only with respiratory infections	35.7
	Not at all	0.0
Question 4: Over the past 4 weeks, I have wheezing attacks	Almost every day	86.2
	Several days a week	71.0
	A few days a month	45.6
	Only with respiratory infections	36.4
	Not at all	0.0
Question 5: How many times during the past 4 weeks have you suffered from severe or very unpleasant respiratory attacks?	More than 3 times	86.7
	3 times	73.5
	2 times	60.3
	1 time	44.2
	None of the time	0.0
Question 6: How long did the worst respiratory attack last? (Go to Question 7 if you did not have a severe attack)	A week or more	89.7
	3 or more days	73.5
	1 or 2 days	58.8

	Less than a day	41.9
Question 7: Over the past 4 weeks, in a typical week, how many good days (with few respiratory problems) have you had?	No good days	93.3
	1 or 2 good days	76.6
	3 or 4 good days	61.5
	Nearly every day was good	15.4
	Every day was good	0.0
Question 8: If you wheeze, is it worse when you get up in the morning?	No	0.0
	Yes	62.0
Part 2		
Question 9: How would you describe your respiratory condition?	The most important problem I have	83.2
	Causes me quite a lot of problems	82.5
	Causes me a few problems	34.6
	Causes no problem	0.0
Question 10: If you ever held a job	My respiratory problems made me stop working altogether	88.9
	My respiratory problems interfere with my job or made me change my job	77.6
	My respiratory problems do not affect my job	0.0
Question 11: Questions about what activities usually make you short of breath these days	Sitting or lying still	90.6
	Washing or dressing yourself	82.8
	Walking around the house	80.2
	Walking outside on level ground	81.4
	Walking up a flight of stairs	76.1
	Walking up hills	75.1
	Playing sports or other physical activities	72.1
Question 12: More questions about your cough and shortness of breath these days	Coughing hurts	81.1
	Coughing makes me tired	79.1
	I am short of breath when I talk	84.5
	I am short of breath when I bend over	76.8

[REDACTED]
 [REDACTED]
 [REDACTED]
 [REDACTED]

	My coughing or breathing disturbs my sleep	87.9
	I get exhausted easily	84.0
Question 13: Questions about other effects your respiratory problems may have on you these days		
	My cough or breathing is embarrassing in public	74.1
	My respiratory problems are a nuisance to my family, friends or neighbors	79.1
	I get afraid or panic when I cannot catch my breath	87.7
	I feel that I am not in control of my respiratory problems	90.1
	I do not expect my respiratory problems to get any better	82.3
	I have become frail or an invalid because of my respiratory problems	89.9
	Exercise is not safe for me	75.7
	Everything seems too much of an effort	84.5
	Question 14: Questions about your respiratory treatment	
My treatment does not help me very much		88.2
I get embarrassed using my medication in public		53.9
I have unpleasant side effects from my medication		81.1
My treatment interferes with my life a lot		70.3
Question 15: Questions about how activities may be affected by your respiratory problems		
	I take a long time to get washed or dressed	74.2
	I cannot take a bath or shower, or I take a long time	81.0
	I walk more slowly than other people, or I stop to rest	71.7

	Jobs such as housework take a long time, or I have to stop to rest	70.6
	If I walk up one flight of stairs, I have to go slowly or stop	71.6
	If I hurry or walk fast, I have to stop or slow down	72.3
	My breathing makes it difficult to do things such as walk up hills, carry things up stairs, light gardening such as weeding, dance, play bowls or play golf	74.5
	My breathing makes it difficult to do things such as carry heavy loads, dig in the garden or shovel snow, jog or walk briskly (5 miles per hour), play tennis or swim	71.4
	My breathing makes it difficult to do things such as very heavy manual work, ride a bike, run, swim fast, or play competitive sports	63.5
Question 16: We would like to know how your respiratory problems usually affect your daily life		
	I cannot play sports or other physical activities	64.8
	I cannot go out for entertainment or recreation	79.8
	I cannot go out of the house to do the shopping	81.0
	I cannot do household chores	79.1
Question 17: Tick the statement which you think best describes how your respiratory problems affect you		
	I cannot move far from my bed or chair	94.0
	It does not stop me from doing anything I would like to do	0.0
	It stops me from doing one or two things I would like to do	42.0
	It stops me from doing most of the things I would like to do	84.2

[REDACTED]
 [REDACTED]
 [REDACTED]
 [REDACTED]

	It stops me from doing everything I would like to do	96.7
--	--	------

[REDACTED]

[REDACTED]

[REDACTED]

[REDACTED]

[REDACTED]

APPENDIX 6. EQ-5D-5L WEIGHTS

To account for this study collecting data in multiple countries, different EQ-5D-5L weights will be used depending on the country, as presented in Table 5.

Table 5: EQ-5D-5L geographical region categorisation

Countries	Version used
Eastern Europe: Bulgaria, Czech Republic, Greece, Hungary, Poland, Romania, Russian Federation, Slovakia	Poland (EQ-VT v2.0)
Western Europe: Germany, United Kingdom	England (EQ-VT v1.0)\
North America: US	US (EQ-VT v2.0)
Asia: Republic of Korea	South Korea (EQ-VT v2.0)

Data collected from questionnaire will be numbered, as presented in Table 6.

Table 6: EQ-5D-5L data collection

Variable name	Mobility	Self-care	Usual Activities	Pain/Discomfort	Anxiety/Depression	Health score	VAS
Variable score range	1-5	1-5	1-5	1-5	1-5	5-digit code for EQ-5D-5L	0-100
Data row example	2	3	1	1	1	23111	83

The health score is a combination of the scores for the 5 questions (mobility, self-care, usual activities, pain/discomfort and anxiety/depression) in the order they are collected, as shown in the data row example in Table 6.

POLAND

The health index is calculated by first summing all weights related to the scores from the questionnaire and subtracting it from 1, i.e. for data row example in Table 6 the health index would be 0.928. Weights related to each score are presented in Table 7.

Table 7: Weights

Variable	Score	Weights
Mobility	1	0
	2	0.025
	3	0.034
	4	0.126
	5	0.314
Self-care	1	0
	2	0.031
	3	0.047
	4	0.111
	5	0.264
Usual Activities	1	0
	2	0.023
	3	0.040
	4	0.097
	5	0.205
Pain/discomfort	1	0
	2	0.030
	3	0.050
	4	0.261
	5	0.575
Anxiety/ depression	1	0

[REDACTED]

[REDACTED]

[REDACTED]

[REDACTED]

[REDACTED]

	2	0.018
	3	0.029
	4	0.108
	5	0.232

ENGLAND

The health index is calculated by first summing all weights related to the scores from the questionnaire and subtracting it from 1, i.e. for data row example in Table 6 the health index would be 0.879. Weights related to each score are presented in Table 8.

Table 8: Weights

Variable	Score	Weights
Mobility	1	0
	2	0.058
	3	0.076
	4	0.207
	5	0.274
Self-care	1	0
	2	0.050
	3	0.080
	4	0.164
	5	0.203
Usual Activities	1	0
	2	0.050
	3	0.063

[REDACTED]

[REDACTED]

[REDACTED]

[REDACTED]

[REDACTED]

[REDACTED]

[REDACTED]

[REDACTED]

[REDACTED]

[REDACTED]

	4	0.162
	5	0.184
Pain/discomfort	1	0
	2	0.063
	3	0.084
	4	0.276
	5	0.335
Anxiety/ depression	1	0
	2	0.078
	3	0.104
	4	0.285
	5	0.289

US

The health index is calculated by first summing all weights related to the scores from the questionnaire and subtracting it from 1, i.e. for data row example in Table 6 the health index would be 0.797. Weights related to each score are presented in Table 9.

Table 9: Weights

Variable	Score	Weights
Mobility	1	0
	2	0.096
	3	0.122
	4	0.237
	5	0.322

[Redacted content]

Self-care	1	0
	2	0.089
	3	0.107
	4	0.220
	5	0.261
Usual Activities	1	0
	2	0.068
	3	0.101
	4	0.255
	5	0.255
Pain/discomfort	1	0
	2	0.060
	3	0.098
	4	0.318
	5	0.414
Anxiety/ depression	1	0
	2	0.057
	3	0.123
	4	0.299
	5	0.321

[REDACTED]

[REDACTED]

[REDACTED]

[REDACTED]

[REDACTED]

[REDACTED]

[REDACTED]

[REDACTED]

SOUTH KOREA

The value for health state is calculated by first summing all weight related to the score from the questionnaire and subtracting it from 1, i.e. for data row example in Table 6 the value for health state would be 0.875. Weights related to each score are presented in Table 10.

Table 10: Weights

Variable	Score	Weights
Mobility	1	0
	2	0.063
	3	0.081
	4	0.159
	5	0.268
Self-care	1	0
	2	0.047
	3	0.062
	4	0.095
	5	0.137
Usual Activities	1	0
	2	0.038
	3	0.074
	4	0.127
	5	0.191
Pain/discomfort	1	0
	2	0.052
	3	0.068
	4	0.175
	5	0.226
Anxiety/ depression	1	0
	2	0.042
	3	0.065
	4	0.131
	5	0.157

[REDACTED]

[REDACTED]

[REDACTED]

[REDACTED]

[REDACTED]

[REDACTED]

[REDACTED]

[REDACTED]

[REDACTED]

[REDACTED]

[REDACTED]

: 12/7/2022 5:17:34 AM

Signer Events	Signature	Timestamp
----------------------	------------------	------------------

Accepted: 12/7/2022 5:17:29 AM
ID: a0329438-4184-4e0c-8f5d-0d1ced879e78
Company Name: IQVIA

In Person Signer Events	Signature	Timestamp
--------------------------------	------------------	------------------

Editor Delivery Events	Status	Timestamp
-------------------------------	---------------	------------------

Agent Delivery Events	Status	Timestamp
------------------------------	---------------	------------------

Intermediary Delivery Events	Status	Timestamp
-------------------------------------	---------------	------------------

Certified Delivery Events	Status	Timestamp
----------------------------------	---------------	------------------

Carbon Copy Events	Status	Timestamp
---------------------------	---------------	------------------

Witness Events	Signature	Timestamp
-----------------------	------------------	------------------

Notary Events	Signature	Timestamp
----------------------	------------------	------------------

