Moderate/severe exacerbations occurring after the day used as offset will not be considered in the analysis. The treatment difference from the negative binomial model will be expressed as an

[REDACTED]

annualized risk ratio. The data will also be summarized by treatment group over duration of the study period. Only moderate/severe COPD exacerbations meeting the protocol-specified criteria will be presented in the listing.

Time to study medication withdrawal or study withdrawal will be presented per stratum and by the following subgroups: patients who withdrew from study medication/study before Week 24 visit and patients who withdrew from study medication/study before Week 48 visit for 48-week stratum.

Time to first moderate/severe COPD exacerbation during the study period will be presented for all patients using full study length, all patients using data truncated at week 24 visit, and patients in 48-week stratum. The primary analysis will include log-rank test stratified by region, actual background medication strata and actual smoking strata. Summary of number of patients with events and number of patients censored will be presented. Outcome will be visualized using a Kaplan-Meier plot.

The health index and VAS score for EQ-5D-5L questionnaire will be analyzed using ANCOVA approach, as described in Section 16.1.3 of the SAP, with data imputation described in Section 16.2.2.3 of the SAP.

HRU over a period truncated up to Week 24 visit for all patients (24-week and 48-week strata combined) and for 48-week stratum only will be summarized for each event and for overall count. HRU during follow-up period will not be presented.

- Sensitivity analysis or subgroup analysis may be considered following results of the patient perception survey. The survey will be summarized to investigate if there are any signs of breaching of the blind related to the appearance of study medication.
- Proportion of E-RS total score responders will be analyzed by means of a logistic regression model with fixed effects for treatment, region, actual background medication strata and actual smoking strata at baseline and baseline E-RS total score as covariate. Missing data will be imputed as described in Section 16.2.2.3 (range method).

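### EQ-5D-5L index: the England worked example (0.879) contradicts its own weights (0.862), and four differently scaled value sets are pooled with no common-set analysis planned

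*SAP*

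**What the plan says.** SAP Appendix 6 states that "different EQ-5D-5L weights will be used depending on the country, as presented in Table 5". Table 5 of that appendix assigns the Polish set to Bulgaria, Czech Republic, Greece, Hungary, Poland, Romania, the Russian Federation and Slovakia; the English set to Germany and the United Kingdom; the US set to the United States; and the South Korean set to the Republic of Korea. The scoring rule is the same for all four: "The health index is calculated by first summing all weights related to the scores from the questionnaire and subtracting it from 1".

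Each set has a worked example for state 23111 (mobility 2, self-care 3, the rest 1). For England the text reads: "for data row example in Table 6 the health index would be 0.879". The others are 0.928 (Poland), 0.797 (US) and 0.875 (South Korea).

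SAP Section 16.3.3 then says: "The health index and VAS score for EQ-5D-5L questionnaire will be analyzed using ANCOVA approach, as described in Section 16.1.3 of the SAP". That model has treatment, region, background medication and smoking as fixed effects and baseline as covariate. Region has three levels (Asia, Europe, North America; Sections 7.1 and 7.2). Missing EQ-5D-5L data are imputed by the range method of Section 16.2.2.3, which bounds the draws with MIN= and MAX= options; no bounds are stated for the index. The only EQ-5D-5L sensitivity analysis (Section 16.3.4) is one without imputation. Protocol Section 3.2.3 lists the questionnaire among the other endpoints, at Week 12.

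**The concern.** There are two separate matters.

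- **England example.** It is the only worked value in the SAP for scoring UK and German patients, and it does not follow from the table printed with it. Either the example or a weight in Table 8 is wrong. If the program carries the wrong weight, every UK or German index at self-care level 3 is affected.
- **Pooled scales.** A main effect for region absorbs differences in level between regions. It does not make a unit of change in one value set equal to a unit in another, and Europe itself contains both Polish-scored and English-scored countries. The single reported utility difference then mixes the drug's effect on the five answers with the mix of countries recruited. The imputation has the same difficulty, since it treats the four indices as one variable with one set of bounds and has region, but not value set, as a predictor.

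**Working it through.** **Inputs.** Weights from Tables 7 (Poland), 8 (England), 9 (US) and 10 (South Korea) of SAP Appendix 6. Index = 1 minus the sum of the five weights.

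**Step 1: reproduce the worked examples for 23111.** Level 1 weighs 0, so only mobility 2 and self-care 3 count.

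| Set | Calculation | Result | SAP states |
|---|---|---|---|
| Poland | 1 - 0.025 - 0.047 | 0.928 | 0.928 |
| US | 1 - 0.096 - 0.107 | 0.797 | 0.797 |
| South Korea | 1 - 0.063 - 0.062 | 0.875 | 0.875 |
| England | 1 - 0.058 - 0.080 | **0.862** | **0.879** |

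The England gap is 0.879 - 0.862 = 0.017. Swapping the two levels (32111) gives 1 - 0.076 - 0.050 = 0.874, so that is not the cause. The stated value equals 1 - 0.058 - 0.063, and 0.063 is Table 8's weight for usual activities level 3 and also for pain level 2. Across all 3,125 states, only 21311 and 21121 score 0.879 in Table 8. A lookup in the wrong row is the likely cause. However, 0.063 would also fit in order between self-care level 2 (0.050) and level 4 (0.164), so the documents alone cannot rule out an error in Table 8.

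**Step 2: value of the same change in each set** (difference in summed weights).

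| Change | Poland | Korea | England | US | Largest / smallest |
|---|---|---|---|---|---|
| 22222 to 11111 | 0.127 | 0.242 | 0.299 | 0.370 | 2.91 |
| 33333 to 22222 | 0.073 | 0.108 | 0.108 | 0.181 | 2.48 |
| Mobility 2 to 1 | 0.025 | 0.063 | 0.058 | 0.096 | 3.84 |
| Anxiety 2 to 1 | 0.018 | 0.042 | 0.078 | 0.057 | 4.33 |
| 55555 to 44444 | 0.887 | 0.292 | 0.191 | 0.244 | 4.64 |

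The ratio depends on the transition, and so does the order: Poland gives the smallest value in the mild changes and the largest in the most severe one.

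**Step 3: dependence on country mix.** The documents give no enrolment shares, so these are assumptions: England 10%, Korea 5%, US varied, the Polish set taking the rest. If every patient moved from 22222 to 11111, the share-weighted mean change (ignoring covariate adjustment) would be:

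- US 15%, Poland 70%: 0.70 x 0.127 + 0.10 x 0.299 + 0.15 x 0.370 + 0.05 x 0.242 = 0.186
- US 30%, Poland 55%: 0.070 + 0.030 + 0.111 + 0.012 = 0.223
- US 45%, Poland 40%: 0.051 + 0.030 + 0.167 + 0.012 = 0.259 (summed before rounding)

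The same answers from every patient give 0.186 to 0.259, according to mix alone.

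**Step 4: imputation bounds.** The lowest possible index, state 55555, is 1 minus the sum of the level 5 weights:

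- Poland: 1 - 1.590 = -0.590
- South Korea: 1 - 0.979 = 0.021
- England: 1 - 1.285 = -0.285
- US: 1 - 1.573 = -0.573

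A single MIN of -0.590 allows impossible values for Korean and English patients. A single MIN of 0.021 excludes valid values in the other three sets.

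**The case against.** The best defence is that country-specific scoring is deliberate: Appendix 6 gives the multi-country setting as its reason. All four sets put full health at 1, and a country-weighted average of nationally valued changes is a usable summary. EQ-5D-5L lies outside the testing hierarchy of SAP Section 7.4. The VAS, which needs no value set, is analysed alongside by the same model, and the five answers are listed, so rescoring stays possible. The England figure is an illustration, while Table 8 governs, so it affects results only if someone builds or validates code against it.

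All of that stands, and it keeps the point small. It does not reconcile 0.879 with Table 8, supply an analysis on one scale, or give imputation bounds that fit four sets.

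A reader might go further in three ways that the documents do not support:

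- **That the test is invalid.** Treatment is randomised and both arms within a country are scored with the same set, so pooling does not bias the comparison under no effect.
- **That US patients dominate the result.** This needs enrolment shares, which are not given, and mild health states; at severe levels the Polish set gives the larger changes. No loss or gain in power can be stated for the same reasons.
- **That 2.9-fold is the upper limit.** It belongs to one transition; some single-item changes exceed it.

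**Conclusion.** The England example is wrong as written: 0.862 follows from the SAP's own rule and table, against 0.879 stated. Which of the two is at fault cannot be settled from the documents, although the three examples that reproduce show that the formula is not in doubt. If a program did carry 0.063 for self-care level 3, a UK or German patient improving from level 3 to level 2 would be credited with 0.063 - 0.050 = 0.013 instead of 0.080 - 0.050 = 0.030.

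The pooling of four value sets is a weakness of scale and interpretation that is cheap to remedy, not an error of inference. The same change is worth 0.127 to 0.370 depending on country for 22222 to 11111, so the size of the pooled index difference cannot be read without knowing the country mix. The weights are the SAP's own; only the shares used to illustrate mix are assumed. The consequence is limited to how the health-utility result of an other endpoint is reported and used.

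**What to change.** 1. Check Table 8 and the England scoring program against the value-set source. Correct whichever is wrong; if Table 8 is confirmed, change the example to 0.862.
2. Before unblinding, name one value set from Appendix 6. Add an analysis of the index with all patients scored, and missing data imputed, on that set, and report it beside the country-specific analysis. The set must be named in advance because the size of the estimate depends on it.
3. If country-specific scoring is kept for the imputed analysis, set the imputation limits by value set and state them. While editing, correct Section 16.3.2, which sends EQ-5D-5L to a Section 16.2.2.13 that does not exist; Section 16.3.3 points to 16.2.2.3.

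**Cost:** one source check, one more derived variable, one more analysis and some SAP wording; no new data. **Downside:** the common-set result does not reflect national preferences and depends on the set chosen, which is why the country-specific analysis should stay beside it.
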